10.1.6 Adverse Events

Please refer to the current version of the Investigator's Brochure for a complete list of adverse events.

Pembrolizumab is generally well tolerated and demonstrates a favorable safety profile in comparison to chemotherapy. Pembrolizumab is an immunomodulatory agent, and based on this mechanism of action, immune mediated adverse events (IMAEs) are of primary concern. Important identified risks for pembrolizumab are of an immune mediate nature, including pneumonitis, colitis, hypophysitis (including hypothyroidism/hyperthyroidism), hepatitis, Type I diabetes mellitus, uveitis, and nephritis, myositis, Guillain-Barre syndrome, pancreatitis, and severe skin reaction toxic epidermal necrolysis (TEN), some with fatal outcome. A new important risk of myocarditis has been identified; cases with fatal outcome have been reported.

The majority of IMAEs was mild to moderate in severity, manageable with appropriate care, and rarely required discontinuation of therapy.

11 ADVERSE EVENTS

The descriptions and grading scales found in the NCI CTCAE v4 will be utilized for AE assessment. A copy of the CTCAE v4 can be downloaded from the CTEP website at <http://ctep.cancer.gov>. All forms for AE/SAE recording and reporting can be found in the Study Procedure Manual or in the EDC system (Documents and Information Tab).

11.1 Definition of Adverse Events

11.1.1 Adverse Event

An adverse event (AE) is any untoward medical occurrence whether or not considered related to the study drug that appears to change in intensity during the course of the study. The following are examples of AEs:

- Unintended or unfavorable sign or symptom
- A disease temporally associated with participation in the protocol

- An intercurrent illness or injury that impairs the well-being of the subject

Abnormal laboratory values or diagnostic test results constitute AEs only if they induce clinical signs or symptoms or require treatment or further diagnostic tests. Hospitalization for elective surgery or routine clinical procedures that are not the result of an AE (e.g., surgical insertion of central line) should not be recorded as an AE.

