10. History or current evidence of any condition, therapy, or laboratory abnormality that might confound the results of the trial, interfere with the subject's participation for the full duration of the trial, or is not in the best interest of the subject to participate, in the opinion of the site investigator.
11. Known psychiatric or substance abuse disorders that would interfere with cooperation with the requirements of the trial.
12. Pregnant or breastfeeding, or expecting to conceive or father children within the projected duration of the trial, starting with the screening period through 120 days after the last dose of protocol therapy.
13. Prior therapy with an anti-PD-1, anti-PD-L1, anti-PD-L2, anti-CD137, or anti-Cytotoxic T-lymphocyte-associated antigen-4 (CTLA-4) antibody (including ipilimumab or any other antibody or drug specifically targeting T-cell co-stimulation or checkpoint pathways). Examples include nivolumab, MPDL3280, etc.
14. Known history of Human Immunodeficiency Virus (HIV) (HIV 1/2 antibodies).
15. Known active Hepatitis B (e.g., HBsAg reactive) or Hepatitis C (e.g., HCV RNA [qualitative] is detected).
16. Receipt of a live vaccine within 30 days prior to registration for protocol therapy. (See Section 5.1.3 for an example list of live vaccines)

17. Unresolved toxicity (i.e., > Grade 1 or above baseline) due to previously administered agents. Exception includes: subjects with \leq Grade 2 neuropathy are eligible for the study.

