11.1.2 Serious Adverse Event

A serious adverse event (SAE) is any untoward medical occurrence resulting in one or more of the following:

- Results in death **NOTE:** Death due to disease progression should not be reported as a SAE, unless it is attributable by the site investigator to the study drug(s)
- Is life-threatening (defined as an event in which the subject was at risk of death at the time of the event; it does not refer to an event which hypothetically might have caused death if it were more severe)
- Requires inpatient hospitalization or prolongation of existing hospitalization
- Results in persistent or significant disability/incapacity
- Is a congenital anomaly or birth defect
- Is an important medical event (defined as a medical event(s) that may not be immediately life-threatening or result in death or hospitalization but, based upon appropriate medical and scientific judgment, may jeopardize the subject or may require intervention (e.g., medical, surgical) to prevent one of the other serious outcomes listed in the definition above). Examples of such events include, but are not limited to, intensive treatment in an emergency room or at home for allergic bronchospasm; blood dyscrasias or convulsions not resulting in hospitalization; or the development of drug dependency or drug abuse.

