11.2 Reporting

11.2.1 AE Reporting

- AEs will be recorded from time of signed informed consent until 30 days after discontinuation of study drug(s).
- AEs will be recorded regardless of whether or not they are considered related to the study drug(s).
- All AEs will be recorded in the subject's medical record and on the appropriate study specific eCRF form within the EDC system.
- AEs considered related to study drug(s) will be followed until resolution to \leq Grade 1 or baseline, deemed clinically insignificant, and/or until a new anti-cancer treatment starts, whichever occurs first.

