12.3 Definitions of secondary endpoints

- PFS, which is defined as the time from randomization to death or progression, depending on which occurs first as defined by RECIST 1.1.
- PFS as per irRECIST and RECIST 1.1 by PD-L1 expression levels.
- Six-month PFS rate, which is defined as the percentage of participants that are alive and progression-free, as per irRECIST and RECIST 1.1, at six months calculated from the date of randomization.
- Six-month PFS rate as per irRECIST and RECIST 1.1 by PD-L1 expression levels.
- Safety of pembrolizumab, defined as rates of Grade 1-5 toxicity according to CTCAE v4.0.
- Objective response rate (ORR) in subjects on maintenance pembrolizumab versus placebo, which is defined by irRECIST and RECIST 1.1 in subjects with measurable disease.
- ORR in subjects receiving pembrolizumab after progressing on placebo as per irRECIST and RECIST 1.1.
- Overall survival (OS), which is defined as the time from randomization to death.

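### The adverse event definition turns on a change in intensity, with no limb for new onset and no limit to worsening, so low-grade events may be recorded inconsistently and improving chemotherapy toxicity counted

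*Combined protocol and SAP*

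**What the plan says.** Section 11.1.1 gives the operative definition of an adverse event: "any untoward medical occurrence whether or not considered related to the study drug that appears to change in intensity during the course of the study". It then lists examples, among them "Unintended or unfavorable sign or symptom" and "A disease temporally associated with participation in the protocol". None of the examples mentions a change in intensity.

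Section 11.1.2 defines the serious event separately: "A serious adverse event (SAE) is any untoward medical occurrence resulting in one or more of the following". The intensity clause is absent there.

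Section 11.2.1 sets the recording window, from consent to 30 days after study drug stops, and says that relatedness does not matter for recording. It does not restate what an adverse event is.

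Section 12.3 lists the secondary endpoint as "Safety of pembrolizumab, defined as rates of Grade 1-5 toxicity according to CTCAE v4.0". Section 12.6 summarizes adverse events by grade in the safety set, as counts and percentages. It has no treatment-emergent rule and no comparison with baseline grade.

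On toxicity carried into the trial, Section 3.2 (exclusion 17) bars "Unresolved toxicity (i.e., > Grade 1 or above baseline) due to previously administered agents" but admits neuropathy up to Grade 2. Section 3.1 (inclusion 7) has subjects starting 2 to 6 weeks after their last first-line chemotherapy.

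**The concern.** The usual test for an adverse event is whether something untoward is new, or is worse than it was. This definition asks only whether intensity changed. Onset is not named, and direction is left open.

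The population makes this more than a stylistic matter. Subjects have recently finished platinum chemotherapy and may still have low-grade toxicity from it. Recording starts at consent, before any study drug, so these effects fall inside the window. Many will ease with time. A site that follows the sentence as written would enter the easing as an event, and Section 12.6 has no rule to remove it from the tables.

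New mild toxicity is the opposite risk. Section 10.1.6 describes most immune-mediated events as mild to moderate, which is where the separate serious-event definition is least likely to catch them. If some sites require a grade change after onset and others do not, the Grade 1-2 rates will partly reflect site practice.

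**Working it through.** The point concerns wording, and the plan states no figure to reproduce. The check is to apply each available reading of Section 11.1.1 to typical cases.

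**Inputs**
- Definition and examples: Section 11.1.1.
- Residual toxicity allowed at entry: Section 3.2, exclusion 17 (Grade 1; neuropathy up to Grade 2).
- Recording window: Section 11.2.1.
- Tabulation rule: Section 12.6.

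**Is the case an adverse event?**

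| Case | Onset counts as a change | Onset does not count as a change | Examples control | New or worse than baseline |
|---|---|---|---|---|
| New toxicity, starts and stays at Grade 1 | Yes | No | Yes | Yes |
| New toxicity, starts at Grade 1 and resolves | Yes | Yes, by resolving | Yes | Yes |
| Baseline Grade 1 toxicity rising to Grade 2 | Yes | Yes | Yes | Yes |
| Baseline neuropathy easing from Grade 2 to Grade 1 | Yes | Yes | Yes | No |
| Baseline neuropathy staying at Grade 2 | No | No | Arguably yes | No |

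**What follows**
1. The easing neuropathy counts under all three readings of the present text. This fault does not depend on how onset is treated.
2. The stable new toxicity is lost under one reading only. The section's examples support the other two.
3. Letting the examples control does not repair the section. They carry no condition on change at all, so an unchanged baseline symptom would also fit. The definition and its examples disagree.
4. No later section settles the matter. Section 11.2.1 deals with timing and relatedness, Section 12.6 with tabulation by grade. Sections 11.1.3 and 11.1.4 build their terms on the same definition.

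**Does it reach the stopping rule?** Section 12.8 uses lower limits of two-sided 90% exact binomial intervals: the 5% quantile of Beta(x, n − x + 1) for x events in n subjects.

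| Criterion | Limit to exceed | Stated boundary | Lower limit there | Lower limit at one event fewer |
|---|---|---|---|---|
| Definitely related death, n = 25 | 0.9% | 2 | 1.44% | 0.20% |
| Definitely related death, n = 50 | 0.9% | 3 | 1.66% | 0.72% |
| Related Grade 4 event, n = 25 | 10% | 6 | 11.0% | 8.2% |
| Related Grade 4 event, n = 50 | 10% | 10 | 11.3% | 9.7% |

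All four boundaries reproduce, and none depends on the clause. Deaths come under the serious-event definition, apart from deaths from progression that are not attributed to study drug. Easing chemotherapy toxicity cannot add Grade 4 events, because entry caps it at Grade 1, or Grade 2 for neuropathy.

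**The case against.** The strongest reply is that the text is clumsy but workable. Going from absent to present is the plainest change in intensity there is, and the examples treat any unfavorable sign or symptom as an event. On that view a new stable rash is plainly included. This stands in part: a reader might infer that such toxicity is excluded outright, and the documents do not support that. They support only that the sentence can be read that way.

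On improvement, it can be said that an easing symptom is hardly untoward, and that Sections 11.2.1 and 11.2.2.1 treat a fall to Grade 1 or baseline as resolution. But in the definition the untoward occurrence is the neuropathy itself, and the change is something that happens to it. The follow-up rules say when an event already recorded is closed. They do not say what may be recorded.

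Recording at screening, and the relatedness categories in Section 11.1.6, would let an analyst separate residual chemotherapy effects. That is true, but Section 12.6 does not ask for it.

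Section 11 places the recording forms in the Study Procedure Manual or the electronic data capture system, neither of which is available here. They may already ask for new or worsening events. For that reason the effect on the data is a possibility, not a finding.

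A reader might also infer that the wording shrinks the contrast with placebo by a calculable amount, perhaps using the melanoma rates in Table 1. The documents do not support this. They do not say what share of events start and stay at one grade, or how sites apply the clause, and Section 12.6 plans no between-arm test of safety.

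**Conclusion.** The definition is wrong as written, and the consequence is minor. Two faults stand: it admits improvement of a baseline condition, and it conflicts with its own examples on whether new onset is enough. The first holds under every reading of the section. The second depends on the reading.

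The part of the safety endpoint exposed is mainly Grades 1 and 2, which may be recorded inconsistently across up to 30 centers and may include resolving chemotherapy toxicity. The serious-event definition and the Section 12.8 boundaries are outside the problem. No size can be given from the documents.

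The conclusion assumes that at least some sites follow the protocol sentence and that no form or manual overrides it. It does not say that the safety results are distorted, only that the text permits it and nothing in the analysis plan corrects it.

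**What to change.** Three short changes:
- In Section 11.1.1, replace the intensity clause so that an adverse event is an untoward occurrence, related or not, *that appears or worsens in intensity during the course of the study*.
- Add there that improvement of a condition present at baseline is not an adverse event.
- In Section 12.6, state that the tables count events that are new or worse than the subject's baseline grade.

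The cost is a brief protocol correction and a note to sites, with perhaps a few more low-grade entries. Screening assessments under Section 7.1.2 already include adverse events, which gives a place to record the baseline grade. No design feature, sample size or stopping boundary changes.

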Type 1 diabetes mellitus (if new onset, including diabetic ketoacidosis [DKA]) or \geq Grade 3 Hyperglycemia, if associated with ketosis (ketonuria) or metabolic acidosis (DKA)

- For T1DM or Grade 3-4 Hyperglycemia
 - Insulin replacement therapy is recommended for Type I diabetes mellitus and for Grade 3-4 hyperglycemia associated with metabolic acidosis or ketonuria.
 - Evaluate subjects with serum glucose and a metabolic panel, urine ketones, glycosylated hemoglobin, and C-peptide.

Hypophysitis:

- For Grade 2 events, treat with corticosteroids. When symptoms improve to Grade 1 or less, steroid taper should be started and continued over no less than 4 weeks. Replacement of appropriate hormones may be required as the steroid dose is tapered.
- For Grade 3-4 events, treat with an initial dose of IV corticosteroids followed by oral corticosteroids. When symptoms improve to Grade 1 or less, steroid taper should be started and continued over no less than 4 weeks. Replacement of appropriate hormones may be required as the steroid dose is tapered.

Hyperthyroidism or Hypothyroidism:

Thyroid disorders can occur at any time during treatment. Monitor subjects for changes in thyroid function (at the start of treatment, periodically during treatment, and as indicated based on clinical evaluation) and for clinical signs and symptoms of thyroid disorders.

- Grade 2 hyperthyroidism events (and Grade 2-4 hypothyroidism):
 - In hyperthyroidism, non-selective beta-blockers (e.g. propranolol) are suggested as initial therapy.
 - In hypothyroidism, thyroid hormone replacement therapy, with levothyroxine or liothyroinine, is indicated per standard of care.
- Grade 3-4 hyperthyroidism
 - Treat with an initial dose of IV corticosteroid followed by oral corticosteroids. When symptoms improve to Grade 1 or less, steroid taper should be started and continued over no less than 4 weeks. Replacement of appropriate hormones may be required as the steroid dose is tapered.

Hepatic:

- For Grade 2 events, monitor liver function tests more frequently until returned to baseline values (consider weekly).
 - Treat with IV or oral corticosteroids
- For Grade 3-4 events, treat with intravenous corticosteroids for 24 to 48 hours.
- When symptoms improve to Grade 1 or less, a steroid taper should be started and continued over no less than 4 weeks.

Renal Failure or Nephritis:

- For Grade 2 events, treat with corticosteroids.
- For Grade 3-4 events, treat with systemic corticosteroids.

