7.1 Screening

7.1.1 Within 28 days prior to registration for protocol therapy:

- Informed consent prior to research specific testing
- Radiological assessment (CT or MRI of chest, abdomen, and pelvis) with tumor measurements
- Identification of available paraffin embedded block or adequate unstained slides of archived tumor tissue (primary or metastatic based on availability).
 - **NOTE:** if adequate archived tissue is unavailable, excisional or percutaneous core tumor biopsy is required for research purposes.
- OPTIONAL SUB-STUDY ANALYSIS: For subjects who have archival tissue from primary site, and who agree to the exploratory sub-study analysis comparing PD-L1 expression in primary tumor tissue versus metastatic post first-line chemotherapy tumor tissue, perform excisional or percutaneous core tumor biopsy for research.

7.1.2 Within 14 days prior to registration for protocol therapy unless otherwise noted:

- Eligibility evaluation (review of inclusion and exclusion criteria)
- Medical history
- Physical examination
- Vital signs including Blood pressure, Weight [kg] Height [cm] (SCREEN ONLY) and ECOG PS
- Laboratory testing:
 - Complete metabolic profile (CMP) will include: serum chemistries (creatinine, glucose, total protein, blood urea nitrogen [BUN], total carbon dioxide [CO₂], albumin, total bilirubin, alkaline phosphatase, and aspartate transaminase [AST] and alanine transaminase [ALT]) and electrolytes (total calcium, chloride, potassium, sodium).
 - CBC (including platelets, ANC & HGB)
 - PT/INR and aPTT
 - TSH, T3 and T4 tests are done. For T3 and T4, free versus total is at the site investigator's discretion
 - Serum pregnancy test for female subjects of childbearing potential (within three days of registration for protocol therapy).
- Smoking History Questionnaire (Appendix A)
- Charlson Comorbidity Index assessment (See SPM for form)
- Record Adverse Events and concomitant medications

7.2 On Treatment: Day 1 of each Cycle (\pm 3 days) unless otherwise noted:

On Day 1 of each treatment cycle, the following assessments/treatment administrations will occur: (NOTE: For Cycle 1 Day 1 ONLY, required tests do not need to be repeated if done within 7 days prior)

- Physical examination
- Vital signs including Blood pressure and Weight [kg] and ECOG PS
- Laboratory testing:

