 - CMP will include: serum chemistries (creatinine, glucose, total protein, BUN, total CO₂, albumin, total bilirubin, alkaline phosphatase, and AST and ALT) and electrolytes (total calcium, chloride, potassium, sodium)
 - CBC (including platelets, ANC & HGB)
 - TSH, T3 and T4 tests are done on Day 1 of even numbered cycles only (i.e., Cycle 2, 4, 6, etc.). For T3 and T4, free versus total is at the site investigator's discretion
 - Correlative studies: Blood sample collection (See Table 7 above for correlative sample schedule)
- Record Adverse Events and any changes to concomitant medications
- Restaging CT or MRI of the chest, abdomen, and pelvis is performed after every four cycles of treatment (i.e., approximately every 12 weeks). Make every effort to perform the same imaging modality throughout the study.
- Pembrolizumab or placebo administration (IV)

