12.6 Analysis plan for secondary objectives

PFS will also be compared between Arms A and B using a weighted logrank test. The weight is 0 before month 2 and 1 after month 3. The form of the weight between month 2 and 3 will take a form specified in Equation (5) of Zucker and Lakatos.⁴⁴ This weighted log-rank test is used due to its maximum efficiency. The time points (months 2 and 3) are chosen based on our belief that that treatment is likely to have minimal effect before month 2 and reach its full effect after month 3. We will also compare the PFS using the usual constant weight logrank test. PFS will also be estimated by the Kaplan-Meier method and the estimated curves will be plotted. Median PFS for both groups will be estimated and their two-sided 95% confidence intervals will be constructed.

Comparison of the 6-month PFS between the two arms will be conducted using estimates from the Kaplan-Meier method and the Greenwood formula. The resulting test is a Chi-square type of test⁴³. Subjects will be analyzed as they are randomized, regardless of the treatment that they actually receive. Data at the end of the 12-month follow-up period of the last treated patient will be used for analyses. For the placebo group, data before cross-over will be used for the analyses of primary objective. The evaluable set will be used for this analysis. PFS with respect to PD-L1 expression levels and OS will be estimated by Kaplan-Meier methods and the comparisons will be performed by logrank tests. Their medians will be estimated with 95% confidence intervals. HRs for both PFS and OS will be estimated using Cox proportional hazard models. Covariate effects will be evaluated by Cox proportional hazard models. RMST will be estimated based on the Kaplan-Meier estimates of the survival functions. ORR for pembrolizumab maintenance, placebo, and pembrolizumab after progression on placebo will be summarized by frequencies and percentages. Comparisons of rates will be performed by Pearson's chi-square tests or Fisher's exact tests. Durations of response will be summarized by median (1st, 3rd quartiles) and be compared using Wilcoxon rank sum test. These analyses will be performed using the evaluable set.

Adverse events for the safety of pembrolizumab will be summarized using frequencies and percentages with respect to grade levels. The safety set will be used for these analyses.

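### The 12.3 safety endpoint promises grade 1-5 CTCAE rates, but the 11.1.1 recording rule and the 12.6 analysis leave silent low-grade laboratory abnormalities incompletely counted

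*Combined protocol and SAP*

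**What the plan says.** Section 12.3 lists the endpoint as "Safety of pembrolizumab, defined as rates of Grade 1-5 toxicity according to CTCAE v4.0". Grade 1 is therefore inside it.

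Section 11.1.1 sets the entry condition for laboratory findings: "Abnormal laboratory values or diagnostic test results constitute AEs only if they induce clinical signs or symptoms or require treatment or further diagnostic tests".

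Section 12.6 gives the analysis: "Adverse events for the safety of pembrolizumab will be summarized using frequencies and percentages with respect to grade levels". It uses the safety set. Section 12.8 adds a stopping rule on treatment-related grade 4 AEs and definitely treatment-related deaths. Sections 12.5 to 12.14 contain no shift table, worst-grade table or other summary of laboratory values.

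The values themselves are scheduled. Section 7.2 opens with "On Day 1 of each treatment cycle, the following assessments/treatment administrations will occur" and includes the metabolic panel (CMP, with AST, ALT, bilirubin, creatinine and glucose) and the blood count (CBC). For thyroid function, "TSH, T3 and T4 tests are done on Day 1 of even numbered cycles only". Section 7.1.2 takes all three at screening. The end-of-treatment visit in 7.3.1 repeats CMP and CBC but not thyroid tests.

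**The concern.** The endpoint is stated on the CTCAE scale from grade 1 upwards. For a laboratory finding without symptoms, the recording rule depends instead on whether treatment or further tests were required. Two subjects with the same graded value can be counted differently according to what the site did next. The laboratory series that would settle the grade directly is collected but not used in any planned analysis.

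This matters because 10.1.6 names immune-mediated harms as the primary concern, lists hepatitis, nephritis, thyroid disease and type 1 diabetes among them, and says most such events were mild to moderate. The stopping rule looks only at grade 4 events and deaths, so the 12.3 endpoint is where lower grades are meant to be reported. Table 2 in 3.1 also admits subjects with abnormal values: AST/ALT up to 2.5 x ULN (5 x with liver metastases) and hemoglobin from 8.5 g/dL. Without a shift from screening, abnormality carried over from before treatment cannot be told apart from change on treatment.

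**Working it through.** The plan states no figure for this point, so there is none to reproduce. The check sets the sections against each other and then asks what can be sized.

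**Step 1. Which laboratory events pass the 11.1.1 filter?** An event with no symptoms passes only if it requires treatment or further tests. Table 4, 5.2.1 and 11.7 show when that happens.

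| Finding | Collected | What makes it a recorded event | What can stay uncounted |
|---|---|---|---|
| Liver | Screening, every cycle, end of treatment | Table 4 and 5.2.1 act from grade 2; the 11.7 combined pattern is reportable on values alone | Silent grade 1; silent grade 2 not attributed to pembrolizumab |
| Renal | As liver | Table 4 and 5.2.1 act from grade 2 | As liver |
| Hypothyroidism | Screening, even cycles | Hormone replacement at grade 2-4 | Silent grade 1 |
| Glucose | As liver | New type 1 diabetes, or grade 3-4 hyperglycemia | Silent lower grades with no action |
| Blood counts | As liver | No row in Table 4; other immune-related events start at intolerable or persistent grade 2 | Silent grade 1 and some silent grade 2 |

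The attribution limit comes from 5.2.1, which applies its guidelines when the site investigator judges the event related to pembrolizumab. The trial is blinded and subjects start 2 to 6 weeks after chemotherapy, so some grade 2 values may be put down to another cause. Section 11.1.1 also does not say whether the routine repeat at the next cycle is a further diagnostic test.

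**Step 2. Can the shortfall be sized?** The only grade mix in the documents is Table 1 (melanoma, n = 135). Grade 1-2 counts are all grades minus grade 3-4:

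- AST: 13 - 2 = 11, so 11/13 = 85%
- ALT: 11 - 0 = 11, so 11/11 = 100%
- Hypothyroidism: 11 - 1 = 10, so 10/11 = 91%
- Renal failure: 3 - 2 = 1, so 1/3 = 33%

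Low grades dominate the liver and thyroid rows but not the renal row. These shares do not measure the gap. Table 1 does not separate grade 1 from grade 2, and its entries are drug-related adverse events already recorded under another study's rule.

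**Step 3. Does the rule distort the comparison between arms?** Write each arm's true rate as p = c + s, where c is the part recorded and s the silent part that is not. The reported difference is c_B - c_A = (p_B - p_A) - (s_B - s_A). It is understated only if s_B exceeds s_A, and it is unchanged if they are equal. The documents give neither s.

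**Step 4. Is anything else affected?** The primary endpoint is PFS, and the sample size in 12.5 uses no safety rate. The 12.8 thresholds come from exact two-sided 90% intervals, with lower bound equal to the 0.05 quantile of Beta(x, n - x + 1):

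- Grade 4 AEs against 10%: 6/25 gives 11.0% (5/25 gives 8.2%); 10/50 gives 11.3% (9/50 gives 9.7%).
- Deaths against 0.9%: 2/25 gives 1.44% (1/25 gives 0.20%); 3/50 gives 1.66% (2/50 gives 0.72%).

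All four thresholds reproduce, and none depends on grade 1 or 2 events.

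**The case against.** The strongest reply is that there is no contradiction. Section 11 applies CTCAE v4 to the assessment of AEs, 12.3 gives the range of grades, and 12.6 tabulates AEs by grade. Read together, the endpoint is graded AEs, and limiting laboratory AEs to those that matter clinically is a stated definition. From grade 2, management under Table 4 and 5.2.1 brings most liver, renal and hypothyroid events back in.

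Much of this stands. It narrows the gap to silent grade 1 values and a limited set of silent grade 2 values. It does not close it: 12.3 speaks of toxicity rates from grade 1 without limiting them to recorded AEs, and nothing restores a silent grade 1 value that prompted no action.

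Three stronger readings are tempting, and the documents do not support them.

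- A reader might infer from Table 1 that a reported AST rate could fall from 13/135 = 9.6% to 2/135 = 1.5%. That drops every grade 1-2 event, although grade 2 events generally meet the AE definition here, and it filters a list that had already been through another study's recording rule.
- A reader might infer that the pembrolizumab-placebo difference will be understated or will vary by site. The rule is the same in both arms, and neither effect is shown.
- A reader might infer that 12.6 is the only safety analysis. Section 12.8 also analyses safety, and 13.2 provides quarterly DSMB review.

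**Conclusion.** The point holds in limited form. As written, the plan cannot give complete grade 1-5 rates for laboratory-defined toxicity, because silent grade 1 abnormalities and some silent grade 2 ones enter the count only if they led to action. Most grade 2 or higher liver and renal events and grade 2-4 hypothyroidism are captured. That rests on sites following Table 4 and 5.2.1 and relating the event to pembrolizumab.

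The size is unknown and cannot be derived from the documents. Bias towards either arm is possible but not shown. The consequence is confined to one secondary endpoint. It is worth correcting because the measurements are already scheduled and a placebo arm is there for comparison.

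**What to change.** Leave the 11.1.1 rule in place for AE forms, leave clinical management unchanged, and add to 12.6:

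> For the safety set, scheduled post-baseline CMP and CBC results (Day 1 of each cycle and end of treatment) will be graded from the values where CTCAE v4 gives numeric limits. Worst post-baseline grade and shift from screening grade will be tabulated by arm, with placebo data cut at cross-over. Thyroid results (screening and even-numbered cycles) will be tabulated by arm as shifts against the local reference range. Subjects meeting the 11.7 liver criterion will be counted by arm. These tables supplement the recorded-AE rates for the 12.3 endpoint.

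If the tables are not wanted, the minimum is to restate the 12.3 endpoint as rates of recorded AEs, so that the endpoint and analysis agree.

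No visit or test is added. The cost is a set of tables and possibly data entry. Section 14.2 requires standard-of-care results at minimum in source documents, with only selected items entered in the EDC system, so values and local normal ranges may have to be collected from up to 30 centers. Reported rates of mild toxicity would become slightly less favourable.
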